5.2. Exclusion Criteria

Participants are excluded from the study if any of the following criteria apply:

Medical Conditions

- 15. Have been diagnosed at any time with type 1 diabetes mellitus or latent autoimmune diabetes in adults

16. Have had any episode of severe hypoglycemia (defined as requiring assistance due to neurologically disabling hypoglycemia) within 6 months prior to screening
17. Have had any episode of hyperglycemic hyperosmolar state or diabetic ketoacidosis within 6 months prior to screening
18. Have hypoglycemia unawareness as judged by the investigator
19. Have excessive insulin resistance, defined as having received a total daily dose of insulin >2.0 U/kg at the time of screening
20. Have cardiovascular disease within 6 months prior to screening, defined as stroke, decompensated heart failure (New York Heart Association Class III or IV), myocardial infarction, unstable angina pectoris, or coronary arterial bypass graft
21. Renal:
 - a. History of renal transplantation
 - b. Currently receiving renal dialysis
 - c. Serum creatinine >2.0 mg/dL (177 µmol/L) at screening as measured by the central laboratory
22. Hepatic: Have obvious clinical signs or symptoms of liver disease (excluding nonalcoholic fatty liver disease), acute or chronic hepatitis, cirrhosis, or elevated liver enzyme measurements as indicated below at screening (Visit 1):
 - a. Total bilirubin level (TBL) $\geq 2 \times$ the upper limit of normal (ULN) (except for Gilbert's syndrome) as defined by the central laboratory, or
 - b. Alanine aminotransferase (ALT) $\geq 3 \times$ ULN as defined by the central laboratory, or
 - c. Aspartate aminotransferase (AST) $\geq 3 \times$ ULN as defined by the central laboratory
23. Malignancy: Have active or untreated malignancy, have been in remission from clinically significant malignancy (other than basal cell or squamous cell skin cancer) for less than 5 years, or are at an increased risk for developing cancer or a recurrence of cancer in the opinion of the investigator
24. Have any hypersensitivity or allergy to any of the insulins or excipients used in this trial
25. Hematologic: Have had a blood transfusion or severe blood loss within 90 days prior to screening (Visit 1) or have known hemoglobinopathy, hemolytic anemia, sickle cell anemia, or any other traits known to interfere with the measurement of HbA1c
26. Have presence of clinically significant gastrointestinal disease (for example, clinically active gastroparesis associated with wide glucose fluctuations) in the investigator's opinion
27. Have a history of or are being evaluated for bariatric surgery including Roux-en-Y gastric bypass surgery, gastric banding, and/or gastric sleeve
28. Have any other condition (including known drug or alcohol abuse, or psychiatric disorder including eating disorder) that precludes the participant from following and completing the protocol

Prior/Concomitant Therapy

29. Have used thiazolidinedione, sulfonylurea, pramlintide, or any other oral or injectable medication intended for the treatment of T2D other than as specified in Inclusion criteria [6, 7] within 90 days prior to screening

30. Have been on an insulin treatment regimen that includes Fiasp®, LY900014, degludec, detemir, neutral protamine Hagedorn insulin, regular human insulin, any premixed insulin, insulin human inhalation powder (Afrezza®) or any insulin therapy other than as specified in Inclusion criterion [5] within 90 days prior to screening
31. Have used continuous subcutaneous (SC) insulin infusion therapy within the 90 days prior to screening
32. Glucocorticoid therapy: Receiving chronic (lasting longer than 14 consecutive days) systemic glucocorticoid therapy (including intravenous, intramuscular, SC, or oral, but excluding topical, intraocular, intranasal, intraarticular, and inhaled preparations) or have received such therapy within 8 weeks immediately prior to screening (Visit 1), with the exception of replacement therapy for adrenal insufficiency
33. Have used any weight loss drugs (for example, prescription drugs: lorcaserin, orlistat, phentermine, phentermine/topiramate, naltrexone/bupropion; or over-the-counter weight loss medications) within 90 days prior to screening

Prior/Concurrent Clinical Study Experience

34. Are currently enrolled in any other clinical trial involving an investigational product (IP) or any other type of medical research judged not to be scientifically or medically compatible with this study
35. Have participated, within the last 30 days, in a clinical trial involving an IP. If the previous IP has a long half-life, 3 months or 5 half-lives (whichever is longer) should have passed
36. Have previously completed or withdrawn from this study or any other study investigating LY900014 after receiving at least 1 dose of the IP

Other Exclusions

37. Are investigator site personnel directly affiliated with this study and/or their immediate families. Immediate family is defined as a spouse, parent, child, or sibling, whether biological or legally adopted
38. Are Lilly employees or representatives (including employees, temporary contract workers, or designees responsible for the conduct of the study)
39. Are unable and/or unwilling to provide informed consent, to make themselves available for the duration of the study, or to abide by study procedures

5.3. Lifestyle Considerations

During the study, participants must avoid:

1. Donating blood or blood products
2. Major changes in diet or exercise

5.4. Screen Failures

Individuals who do not meet the criteria for participation in this study (screen failure) may not be rescreened. Retests are also not allowed, except for cases in which results are not available from the original sample.

Screen failures are defined as participants who consent to participate in the clinical study but are not subsequently enrolled in the study. A minimal set of screen failure information is required to ensure transparent reporting of screen failure participants to meet the Consolidated Standards of Reporting Trials (CONSORT) publishing requirements and to respond to queries from regulatory authorities. Minimal information includes demography, screen failure details, eligibility criteria, and any serious adverse event (SAE).

6. Study Intervention

Study intervention is defined as any investigational interventions, marketed products, placebo, or medical devices intended to be administered to a study participant according to the study protocol.

6.1. Study Interventions

Intervention Name	LY900014
Type	Drug
Dose Formulation	Solution
Unit Dose Strength(s)	100 U/mL in 3 mL cartridge
Dosage Level(s)	Individualized dosing
Route of Administration	Subcutaneous
Packaging and Labeling	LY900014 will be provided in prefilled pens. Each pen will be labeled as required per country requirement.
Sourcing	Provided centrally by the sponsor, subsidiary, or designee

6.1.1. Medical Devices

1. The Lilly manufactured medical devices provided for use in this study are:
 - a. the LY900014 prefilled pen, and
 - b. the insulin glargine U-100 (Basaglar) prefilled pen.
2. Instructions for use for each of the prefilled pens will be provided.
3. The FreeStyle Libre is a marketed, non-Lilly, medical device for CGM. It will also be provided to study participants.

6.2. Preparation/Handling/Storage/Accountability

1. The investigator or designee must confirm appropriate temperature conditions have been maintained during transit for all study intervention received and any discrepancies are reported and resolved before use of the study intervention.
2. Only participants enrolled in the study may receive study intervention and only authorized site staff may supply or administer study intervention. All study intervention must be stored in a secure, environmentally controlled, and monitored (manual or automated) area in accordance with the labeled storage conditions with access limited to the investigator and authorized site staff.

3. The investigator, institution, or the head of the medical institution (where applicable) is responsible for study intervention accountability, reconciliation, and record maintenance (that is, receipt, reconciliation, and final disposition records).
4. Further guidance and information for the final disposition of unused study interventions are provided in the Pharmacy Manual.
5. All insulin products must be stored at the investigative site under refrigerated conditions (between 2°C and 8°C) in a locked and secure place. Insulin must not be frozen.
6. In-use insulin should be maintained at room temperature. In-use insulin must not be used after 28 days.

6.3. Measures to Minimize Bias: Randomization and Blinding

This is an open-label, single arm study.

6.4. Study Intervention Compliance

When participants self-administer study intervention(s) at home, compliance with study intervention will be assessed at each visit. Compliance will be assessed by reviewing the participant's glycemic control, adherence to the visit and treatment schedule, use of the study CGM system, adjustment of prandial insulin doses as appropriate, and completion of study diaries. Compliance will be documented in the source documents and the electronic case report form (eCRF).

Participants who are deemed noncompliant will receive additional diabetes education and training, as required, and the importance of compliance with the protocol will be reinforced. Participants who, in the opinion of the investigator, are deemed consistently noncompliant may be discontinued from the study.

6.5. Concomitant Therapy

The following concomitant therapies will not be allowed during the study:

- any oral or injectable medication intended for the treatment of diabetes mellitus other than study insulins and those specified in Section 6.5.1. Exception: short-term use of nonstudy insulins is permissible as outlined in Section 7.1.1.
- chronic (lasting longer than 7 consecutive days) systemic glucocorticoid therapy excluding topical, intraocular, intranasal, inhaled, or intraarticular preparations.
- Weight loss drugs (for example, prescription drugs: lorcaserin, orlistat, phentermine, phentermine/topiramate, naltrexone/bupropion; or over-the-counter weight loss medications)

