1.2. Schema

1.3. Schedule of Activities (SoA)

	Screen	Baseline		Treatment Period											ED
Visit Number	1	2	3	4	5	6	7	8	9	10	11	12	801	ED	
Visit Window (\pm days)		3	3	3	3	3	3	3	3	3	3	3	3	7	
Time (weeks)	-5	-4	-2	0	1	2	4	6	8	10	11	12	14		
Telephone visits are indicated by shaded columns. Telephone visits can become office visits if needed. Site documentation will serve as the source for telephone visits.															
Informed Consent Signed	X														
IWRS	X	X	X	X	X	X	X	X	X	X	X	X	X	X	
Participant eligibility review	X														
Treatment assignment				X											
Note: Treatment assignment should occur after completion of all Visit-4 procedures. Participants who have been assigned treatment will be asked to return for the ED visit.															
Clinical Assessments															
Participant demographics	X														
Medical history and preexisting conditions	X														
Physical exam/height	X														
Concomitant medications	X	X	X	X	X	X	X	X	X	X	X	X	X	X	
Adverse events and product complaints	X	X	X	X	X	X	X	X	X	X	X	X	X	X	
Body weight	X	X		X			X		X			X		X	
Vital signs, blood pressure and heart rate	X	X		X			X		X			X		X	
Note: Vital sign measurements should be determined after participants have been seated quietly for at least 5 minutes in a chair with feet on the floor. The arm used for blood pressure measurement should be supported at heart level.															
ECG (12-lead; local)	X														
Note: Participants must be supine for approximately 5-10 minutes before ECG collection and remain supine, but awake, during ECG collection.															
Diabetes, hypoglycemia and nutrition counseling		X													
Note: Initial training at Visit 2 will include diabetes education and nutrition counseling. Appropriate site personnel will administer training and education using locally approved diabetes education/training materials and programs or by using other materials that may be provided by the sponsor. Participants may be provided abbreviated training and education at visits following Visit 2 as appropriate.															
Basal and prandial insulin dose assessments			X	X	X	X	X	X	X	X	X	X	X	X	

	Screen	Baseline		Treatment Period										ED
		1	2	3	4	5	6	7	8	9	10	11	12	801
Visit Number	1	2	3	4	5	6	7	8	9	10	11	12	801	ED
Visit Window (± days)		3	3	3	3	3	3	3	3	3	3	3	3	7
Time (weeks)	-5	-4	-2	0	1	2	4	6	8	10	11	12	14	

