7.2. Participant Discontinuation/Withdrawal from the Study

Participants will be withdrawn from the study:

- at any time at his/her own request
- at the request of his/her designee (for example, parents or legal guardian)
- at the discretion of the investigator for safety, behavioral, compliance, or administrative reasons
- if participant has not taken IP for more than 14 consecutive days (see Section [7.1.1](#))
- if the participant becomes pregnant during the study
- if enrollment in any other clinical study involving an IP or enrollment in any other type of medical research judged not to be scientifically or medically compatible with this study
- if the investigator, after consultation with the sponsor-designated medical monitor, determines that a systemic hypersensitivity reaction has occurred related to study drug administration
- if the participant, for any reason, requires treatment with another therapeutic agent that has been demonstrated to be effective for treatment of the study indication, discontinuation from the study occurs prior to introduction of the new agent
- use of prohibited concomitant medication (see Section [6.5](#))

Discontinuation is expected to be uncommon.

At the time of discontinuing from the study, if possible, an early discontinuation visit should be conducted, as shown in the SoA. See SoA for data to be collected at the time of study discontinuation and follow-up and for any further evaluations that need to be completed. The participant will be permanently discontinued both from the study intervention and from the study at that time.

If the participant withdraws consent for disclosure of future information, the sponsor may retain and continue to use any data collected before such a withdrawal of consent. If a participant withdraws from the study, he/she may request destruction of any samples taken and not tested, and the investigator must document this in the site study records.

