7.3. Lost to Follow-up

A participant will be considered lost to follow-up if he or she repeatedly fails to return for scheduled visits and is unable to be contacted by the study site. Site personnel are expected to make diligent attempts to contact participants who fail to return for a scheduled visit or were otherwise unable to be followed up by the site.

8. Study Assessments and Procedures

- Study procedures and their timing are summarized in the SoA. Protocol waivers or exemptions are not allowed.
- Immediate safety concerns should be discussed with the sponsor immediately upon occurrence or awareness to determine if the participant should continue or discontinue study intervention.
- Adherence to the study design requirements, including those specified in the SoA, is essential and required for study conduct.
- All screening evaluations must be completed and reviewed to confirm that potential participants meet all eligibility criteria. The investigator will maintain a screening log to record details of all participants screened and to confirm eligibility or record reasons for screening failure, as applicable.

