9.3. Populations for Analyses

The following populations are defined:

Population	Description
Entered	All participants who give informed consent
Enrolled	All participants who continue the study after Visit 2.
Treated	All enrolled participants who receive at least 1 dose of the assigned IP after Visit 4

Abbreviations: IP = investigational product.

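### Protocol Section 6.5 omits the adrenal-replacement exemption that exclusion criterion 32 grants, so read literally Section 7.2 requires withdrawal of an eligible participant

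*Protocol*

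**What the plan says.** Four places in the Protocol bear on this.

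- **Section 5.2, criterion 32 (entry).** It excludes a person who is "Receiving chronic (lasting longer than 14 consecutive days) systemic glucocorticoid therapy", or who had such therapy in the 8 weeks before screening. Certain local routes are left out of the definition. The sentence ends "with the exception of replacement therapy for adrenal insufficiency".
- **Section 6.5 (on study).** Among the therapies not allowed during the study is "chronic (lasting longer than 7 consecutive days) systemic glucocorticoid therapy excluding topical, intraocular, intranasal, inhaled, or intraarticular preparations". The only carve-outs in that bullet are by route.
- **Section 7.2 (withdrawal).** The list of mandatory reasons for withdrawal includes "use of prohibited concomitant medication", with a pointer to Section 6.5.
- **Section 8, opening bullets.** "Protocol waivers or exemptions are not allowed".

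The adrenal-insufficiency exemption appears in criterion 32 and nowhere else in the Protocol or the SAP.

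**The concern.** The entry rule and the on-study rule treat the same participant in opposite ways. A person on long-term systemic replacement passes criterion 32, yet continuing that therapy falls inside the Section 6.5 prohibition, and Section 7.2 turns the prohibition into withdrawal.

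A site that enrols such a person can withdraw a participant who met every criterion, stop a replacement therapy, or keep the participant and record a deviation. Different sites may choose differently. A site that avoids the problem by calling the person a screen failure cannot reverse that, because Section 5.4 does not allow rescreening.

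What is at stake is mainly consistent conduct and the participant's care. The effect on the primary analysis depends on when the rule is enforced.

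**Working it through.** The plan states no figure on this point. The check is a comparison of the rules, followed by a bound on the consequence.

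**1. Comparing the two rules**

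| Feature | Criterion 32 (5.2) | Section 6.5 |
|---|---|---|
| Applies to | Entry | During the study |
| Chronic means more than | 14 consecutive days | 7 consecutive days |
| Local routes excluded | Yes, five | Yes, the same five |
| Adrenal replacement exempt | Yes | Not stated |

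The two time limits cover different periods. A stricter on-study limit may be intended, so that difference is not part of this point. The last row is.

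**2. Can the exemption be read into Section 6.5?** The text does not support it.

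- Criterion 32 needed an express exception to take replacement out of systemic glucocorticoid therapy. Section 6.5 uses the same term without one.
- Section 6.5 states an exception where one is meant. Its first bullet says "Exception: short-term use of nonstudy insulins is permissible as outlined in Section 7.1.1".
- A deliberate ban would leave the criterion 32 exemption with little purpose, since those admitted under it while on ongoing replacement would then have to be withdrawn.

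**3. Is there another written route?** None was found.

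- Section 6.5.1 covers only oral antihyperglycemic drugs and GLP-1 agonists.
- Section 7.2.1 allows the sponsor's physician to approve continuation, but only for someone enrolled without meeting the criteria. This participant met them.
- Section 8 bars waivers.

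**4. When would the rule bite?** The Schedule of Activities (1.3) puts Visit 1 at Week -5, Visit 2 at Week -4 and Visit 4 at Week 0. Visits 2 and 4 each have a window of 3 days either way. Section 6.5 does not say when its count starts, so both starting points are shown. For a participant already on replacement, the limit is passed once 8 days have run:

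- From Visit 1: 5 × 7 = 35 days to Visit 4; 35 − 8 = 27 days to spare (nominal, as no window is given for Visit 1).
- From Visit 2: 4 × 7 = 28 days; 28 − 8 = 20 days to spare.
- From Visit 2 at the shortest spacing: 28 − 3 − 3 = 22 days; 22 − 8 = 14 days to spare.

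**5. Consequence.** On assignment at Visit 4, the Schedule says "Treatment assignment should occur after completion of all Visit-4 procedures". The Treated population (9.3) is "All enrolled participants who receive at least 1 dose of the assigned IP after Visit 4". A participant removed on time is therefore outside both the Treated population and the 167 assigned: 0 of 167 and 0 Week 12 endpoints lost. If a site enforces the rule only after Visit 4, the loss is 1 Week 12 endpoint per affected participant.

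**The case against.** The strongest objection is to the reading of criterion 32. If its closing exception attaches only to the nearest clause, on therapy in the 8 weeks before screening, then current users of replacement are excluded at entry and Section 6.5 conflicts with nothing. The grammar permits this, but it is the less natural reading. A comma sets the exception off from the whole sentence, and replacement is usually ongoing, so an exemption for past use alone would help almost nobody.

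A second objection is that an amendment could keep the participant, since Section 10.1.1 provides for amendments with ethics approval. That is true, but a site cannot amend the protocol itself, and such an amendment is in effect the fix proposed here. The accurate statement is that a site has no permitted route under the current text.

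Third, the insulin exception in the first bullet of 6.5 concerns another drug class and temporary interruption of study drug, so it is weak evidence about the glucocorticoid bullet. That is fair. It supports the reading but does not carry it; the missing clause and the mandatory wording of 7.2 do.

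Fourth, the timing figures depend on an undefined start of the 7-day count, and a site that has just applied the entry exemption may simply keep the participant. This also stands. The figures show only that the limit would normally be passed before Visit 4. They do not predict what sites will do.

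Finally, the documents do not show that any such participant would enrol. That bears on severity, not on whether the rules conflict.

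**Conclusion.** The concern holds. As written, Sections 6.5 and 7.2 together require withdrawal of a participant whom criterion 32 accepts, and no other text in the Protocol or SAP restores the exemption.

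The size is at the low end of minor. The documents do not give the number of participants affected; the assumption here is that it is very small, which makes the effect on the results probably negligible. The endpoint, sample size, population definitions and analysis methods are untouched.

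The conclusion rests on reading the criterion 32 exception as covering current as well as recent therapy, and on taking the prohibition in 6.5 and the withdrawal rule in 7.2 literally.

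**What to change.** In the glucocorticoid bullet of Protocol Section 6.5, add the clause that already closes criterion 32: "with the exception of replacement therapy for adrenal insufficiency". Section 7.2 needs no edit, because it defines prohibited medication by reference to 6.5. The 7-day and 14-day limits can stay as they are.

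The cost is one clause in one bullet, with no effect on design, sample size or analysis.

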6.5.1. Management of Oral Antihyperglycemic Medications and Injectable GLP-1 Agonist

During the study baseline and treatment periods, participants may **continue** the use of:

- up to 3 of the following OAMs for the treatment of T2D: metformin, SGLT2 inhibitor, DPP-4 inhibitor, oral GLP-1 agonist and/or

- an injectable GLP-1 agonist for the treatment of T2D

Please note that participants must have entered the study on these agents with stable dosing for 90 days prior to screening (Section 5.1, Inclusion Criteria [5,6,7]). Please also refer to Section 5.2, Exclusion Criteria [29,30].

Oral antihyperglycemic medications and GLP-1 dosing should remain stable during the study baseline and treatment periods, except with the development of contraindications or for safety reasons. During the study, all glycemic management is to be conducted by adjustment of basal and prandial insulin doses.

